11. REGULATORY CONSIDERATIONS

11.1 Regulatory Oversight

The US Food and Drug Administration (FDA) has not approved ipilimumab nor nivolumab for the treatment of soft tissue sarcoma, however ipilimumab and nivolumab are approved for use in combination by the FDA for several tumor settings. Although the investigator will submit an IND for this study, the FDA may deem the study to be IND-exempt.

This study will only be initiated and conducted after review and approval by the local IRB of record.

11.2 Monitoring plan

The Stanford Cancer Institute Data and Safety Monitoring Committee (DSMC) will be the monitoring entity for this study.

The DSMC will audit study-related activities approximately once per year to determine whether the study has been conducted in accordance with the protocol, local standard operating procedures, FDA regulations, and Good Clinical Practice (GCP). This may include review of the following types of documents participating in the study: regulatory binders, case report forms, eligibility checklists, and source documents. In addition, the DSMC will regularly review serious adverse events and protocol deviations associated with the research to ensure the protection of human subjects. Results of the DSMC audit will be communicated to the IRB and the appropriate regulatory authorities at the time of continuing review, or in an expedited fashion, as needed.

11.3 Protocol Review and Amendments

The protocol, the proposed informed consent and all forms of participant information related to the study (eg, advertisements used to recruit participants) will be reviewed and approved by the Stanford IRB and Stanford Cancer Institute Scientific Review Committee (SRC). Any changes made to the protocol will be submitted as a modification and will be approved by the IRB prior to implementation.

11.4 Data management

The research coordinator will be responsible for database records of subject data. The data will be kept in an OnCore online database, under password protection with access limited to specific areas of the database. A chart with all of the relevant research subject information will be maintained for each subject by the research coordinator. Subject charts will be reviewed by Stanford PI and Study Coordinator for yearly audits.

11.5 Study Documentation

The Protocol Director must maintain adequate and accurate participant case histories with observations and other data pertinent to the study. Original source documents should be transcribed to Case Report Forms (CRFs). Source documents include hospital records, clinical charts, laboratory and pharmacy records, and recorded electronic data.

The Principal Investigator will be responsible for maintaining the clinical protocol and subjects' study charts, reporting adverse events, assuring that consent is obtained and documented, and reporting the status of the trial in continuing renewals submitted to their IRB and trial monitoring group(s).

12. STATISTICAL CONSIDERATIONS

We anticipate enrolling no more than 30 subjects to achieve our aims and this is feasible. Specifically, it is anticipated that 3 to 4 subjects per month may be enrolled onto this trial. Thus, it is expected that 12 months will be required to accrue the number of subjects necessary to complete the trial.

More specifically, clinical benefit (CR/PR/SD) will be assessed for each subject at 16 weeks. Our null hypothesis is that the response rate is $\leq 30\%$, and our alternative

hypothesis is that the response rate is $\geq 60\%$. The selection of 60% as a threshold for determining the treatment is worthy of further study is due to recent trials of sarcoma FDA-approved drugs showing ~60% PFS rate at 3 months (ie, pazopanib, trabectedin, eribulin).

We will employ a Simon 2-stage design to address our primary objective. The type 1 error rate assumed for the Simon 2-stage design is 0.04. The null hypothesis that the true response rate (ie, sum of CR and PR) is 30% or less will be tested against a one-sided alternative. Our decision rule works as follows. In the first stage, we will accrue and assess 10 subjects. If 3 or fewer subjects (< 30% of 10 subjects) achieve a clinical response, the trial will be stopped for futility. If more than 3 subjects achieve a clinical response, we will enroll and treat an additional 18 subjects. If 12 or fewer of the 28 treated subjects (< 42.8%) demonstrate a clinical response (either CR or PR), we will conclude the treatment is not worthy of further study. If, however, more than 12 of the 28 treated subjects ($\geq 42.8\%$) responds, we will claim the treatment promising.

Assuming a true response rate of 60%, we have 90% power to correctly conclude the treatment promising. In contrast, if the true response rate is only 30%, we have a low probability (0.04) of incorrectly continuing to study the treatment.

Additionally, we will characterize rates of toxicity by level of toxicity as well as by other subject-level characteristics.

To address secondary objectives, we will use Kaplan-Meier methods to graphically depict progression-free survival. This tool will also be used to demonstrate survival across various sub-groups of interest. Generalized linear regression methods (with a logit link) will be utilized to characterize relationships between features such as mutation burden, PDL1 expression, and tumor infiltrating lymphocytes and response.

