STATISTICAL CONSIDERATIONS (continued)	
A Simon-2-stage design will be used to address primary objective. The null hypothesis that the true response rate is 30% will be tested against a one-sided alternative. Our decision rule works as follows. In the first stage, we will accrue and assess 10 subjects. If 3 or fewer subjects (< 30% of 10 subjects) achieve a clinical response, the trial will be stopped for futility. If more than 3 subjects achieve a clinical response, we will enroll and treat an additional 18 subjects. If 12 or fewer of the 28 treated subjects (< 42.8%) demonstrate a clinical response (either CR or PR), we will conclude the treatment is not worthy of further study. If, however, more than 12 of the 28 treated subjects ($\geq 42.8\%$) responds, we will claim the treatment promising. Assuming a true response rate of 60%, we have 90% power to correctly conclude the treatment promising. In contrast, if the true response rate is only 30%, we have a low probability (0.04) of incorrectly continuing to study the treatment.
 
Rates of toxicity will be characterized by level of toxicity as well as by other subject-level characteristics.
 
To address secondary objectives, we will use Kaplan-Meier methods to graphically depict PFS. This tool will also be used to demonstrate survival across various sub-groups of interest. Generalized linear regression methods (with a logit link) will be utilized to characterize relationships between features such as mutation burden, PDL1 expression, and tumor infiltrating lymphocytes and response.

--	--

SCHEMA

LIST OF ABBREVIATIONS AND DEFINITION OF TERMS

ADL	Activities of daily living
AE	Adverse event
BID	Twice daily
BSA	Body surface area
CBC	Complete blood count
CI	Confidence interval
CMAX	Maximum concentration of drug
CNS	Central nervous system
CRF	Case report form
CR	Complete response
CTCAE	Common Terminology Criteria for Adverse Events
DLT	Dose Limiting Toxicity
DSMB	Data Safety Monitoring Board
ECG	Electrocardiogram
GI	Gastrointestinal
Hgb	Hemoglobin
HIV	Human Immunodeficiency Virus
HPF	High-power field
HTN	Hypertension
IRB	Institutional Review Board
irRECIST	Immune-related response evaluation criteria in solid tumors (RECIST)
IV	Intravenous
LLN	Lower limit of normal
MIBI	Multiplexed ion beam imaging
NGS	Next generation sequencing
OS	Overall survival
PLT	Platelets
PD	Progressive disease
PFS	Progression free survival
PR	Partial response
QD	Once daily

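### The percentages beside the final decision rule contradict its counts at exactly 12 of 28 responders; the counts reproduce the stated error rates, so only the percentages need correcting

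*Combined protocol and SAP*

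**What the plan says.** Section 12 (Statistical Considerations) sets out a Simon two-stage design with a null response rate of 30% and an alternative of 60%.

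- **Stage 1, 10 subjects:** "If 3 or fewer subjects (< 30% of 10 subjects) achieve a clinical response, the trial will be stopped for futility". Otherwise, "If more than 3 subjects achieve a clinical response, we will enroll and treat an additional 18 subjects".
- **Final analysis, negative branch:** "If 12 or fewer of the 28 treated subjects (< 42.8%) demonstrate a clinical response", the treatment is judged not worth pursuing.
- **Final analysis, positive branch:** "more than 12 of the 28 treated subjects ($\geq 42.8\%$) responds, we will claim the treatment promising".

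The Statistical Considerations entry of the Protocol Synopsis repeats the rule with the same percentages.

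The operating characteristics are given as "The type 1 error rate assumed for the Simon 2-stage design is 0.04" and "Assuming a true response rate of 60%, we have 90% power to correctly conclude the treatment promising". The error rate is then repeated for a true rate of 30%: "we have a low probability (0.04) of incorrectly continuing to study the treatment".

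**The concern.** Each branch of the final rule is stated twice, once as a count and once as a percentage, and the two should select the same outcomes. They do not at 12 responders, the largest count in the negative branch. Its percentage is 42.86%, which fails the label on the branch where the count puts it and satisfies the label on the opposite branch.

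This is the count on which the primary conclusion turns. If the trial ended there, a report giving a 42.9% response rate could cite the printed threshold in support of a positive claim, while the count rule says the opposite. A decision boundary should not allow two readings once the data are known.

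**Working it through.** **Inputs (Section 12).** Null rate 0.30; alternative 0.60; one-sided; 10 subjects in stage 1, stopping at 3 or fewer; 18 more, for 28 in total; positive if more than 12. Stated type I error 0.04 and power 90%.

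**Step 1: percentages at the boundaries.**

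- 12/28 = 0.42857, or 42.86% (42.9% to one decimal).
- 13/28 = 0.46429, or 46.4%. This is the smallest positive count.
- 0.428 × 28 = 11.98, so the smallest whole count meeting a threshold of at least 42.8% is 12, not 13.
- Truncation (42.8 for 42.857) is not the only fault. With the cut-off written exactly as 12/28, a strict less-than would still exclude 12 from the negative branch, and a greater-or-equal would still admit it to the positive one.

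**Step 2: reproduce the stated error rates from the counts.** For a design that continues when stage 1 responders exceed r1 and is positive when total responders exceed r:

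P(positive | p) = Σ over x = r1+1 to 10 of C(10,x) pˣ(1−p)¹⁰⁻ˣ × P(Bin(18,p) ≥ r+1−x)

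With r1 = 3 and r = 12:

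- p = 0.30: 0.0419, which is 0.04 at the printed precision.
- p = 0.60: 0.9122, consistent with the stated 90%.

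**Step 3: follow the final percentage instead.** Keep the stage 1 count and let 12/28 be positive (r1 = 3, r = 11):

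| Final rule | Type I error (p = 0.30) | Power (p = 0.60) |
|---|---|---|
| Counts: positive at 13 or more | 0.0419 | 0.9122 |
| Percentage: positive at 12 or more | 0.0813 | 0.9330 |

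The stated 0.04 therefore belongs to the counts.

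**Step 4: how often the conflict would arise.** The two rules differ only at a total of exactly 12 after passing stage 1, so the difference between the rows is the probability of that outcome:

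- p = 0.30: 0.0813 − 0.0419 = 0.0394.
- p = 0.60: 0.9330 − 0.9122 = 0.0208.

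Among trials that pass stage 1 (probability 0.3504 at p = 0.30 and 0.9452 at p = 0.60), the figures are 0.0394/0.3504 = 0.112 and 0.0208/0.9452 = 0.022.

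The documents posit no rate between 30% and 60%. If one is assumed, the joint probability is 0.1055 at p = 0.40, 0.1077 at 0.45 and 0.0830 at 0.50, with a maximum of 0.111 near 0.43.

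**Step 5: the stage 1 label.** Three of 10 is exactly 30%, so describing 3 or fewer as below 30% is also wrong. No count receives two verdicts there, because the continuation branch is given only as a count, with no percentage.

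**The case against.** The strongest reply is that the operative rule is not ambiguous. The counts are the main clauses, they cover every outcome without overlap, and the percentages are only glosses in brackets. To reach 0.081 a reader would have to override an explicit count, ignore a type I error of 0.04 that Section 12 states twice and the synopsis once, and follow the bracket at the final stage while following the count at stage 1. On this view the defect is a truncated decimal and a wrong inequality sign.

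Most of this stands. The counts should govern, and 0.081 is the result of a misreading, not an expected consequence of the plan. The reply does not make the labels true: both statements of the rule print a threshold that the boundary count falls on the wrong side of. It limits the weight of the point without removing it.

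A second objection concerns the remedy. Restated percentages work only with a denominator of exactly 28, whereas the plan elsewhere gives 30 subjects. If 30 were analysed, 13/30 = 43.3% would fall between at most 42.9% and at least 46.4%, and so under neither label. That is a good reason to prefer deleting the percentages.

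**Conclusion.** The inconsistency is real and minor. At exactly 12 of 28 responders the count and the percentage give opposite verdicts, in both places where the rule is written. The count rule is sound as arithmetic and yields the stated error rates (0.042 and 0.912). Only if exactly 12 responded and the percentage were followed in preference to the count would the rule in use be one with type I error 0.081. At the two response rates the plan uses, the probability of reaching that outcome is 0.039 and 0.021.

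These figures assume exact binomial sampling, 28 evaluable subjects and the stage 1 rule applied by count. The conclusion covers only the arithmetic of the 3/10 and 12/28 rule. It does not settle whether the endpoint is CR plus PR or also includes SD, on which Section 12 is not consistent. Nor does it settle how the 28 in the rule relates to the planned 30 subjects; with 30 analysed and success still at more than 12, type I error would be 0.067.

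**What to change.** In Section 12 and in the synopsis entry, keep the counts and delete the bracketed percentages. This is the cleaner option because it holds whatever denominator is finally reported. If percentages are wanted, restate them to match the counts:

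- stage 1 stop: at most 3/10 (at most 30%);
- final, not promising: at most 12/28 (at most 42.9%);
- final, promising: at least 13/28 (at least 46.4%).

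The cost is a few words in two places. The design, sample size, analysis set and error rates are unaffected.

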12. STATISTICAL CONSIDERATIONS	28
13. REFERENCES.....	30
APPENDICES.....	31
APPENDIX A: PARTICIPANT ELIGIBILITY CHECKLIST	31
APPENDIX B: RECIST 1.1	34
APPENDIX C: IMMUNE-RELATED RESPONSE EVALUATION CRITERIA IN SOLID TUMORS (IMMUNE-RELATED RECIST, IRRECIST)	43
APPENDIX D: TOXICITY MANAGEMENT.....	50
APPENDIX E: ADVERSE EVENTS REPORTING	57
APPENDIX F: PATIENT-REPORTED OUTCOME (PRO) QUESTIONNAIRES	63
APPENDIX REFERENCES.....	92

PROTOCOL SYNOPSIS

TITLE	Phase 2 Study of Ipilimumab Plus Nivolumab in Combination with Cryotherapy in Metastatic or Locally Advanced Soft Tissue Sarcoma
STUDY PHASE	Phase 2
INDICATION	Soft tissue sarcoma
INVESTIGATIONAL PRODUCT OR PROCEDURE	Ipilimumab plus nivolumab in combination with cryotherapy
PRIMARY OBJECTIVE(S)	
 Assess whether the rate of clinical benefit is sufficiently high to merit promise for further study
SECONDARY OBJECTIVE(S)	
 Characterize the 6-month progression-free survival rate Assess whether the treatment yields a reasonably safe and tolerable profile
EXPLORATORY OBJECTIVE(S)	
 Correlate the mutation burden by NGS with response Correlate PDL1 expression with response Correlate tumor infiltrating lymphocytes/macrophages with response
TREATMENT SUMMARY	
 Ipilimumab 1 mg/kg and nivolumab 3 mg/kg every 3 weeks for 4 doses followed by nivolumab 480 mg every 4 weeks until progression or intolerance (maximum 24 months). Cryoablation of at least one tumor mass between Cycle 1 and 2 of above immunotherapy
SAMPLE SIZE	30
STATISTICAL CONSIDERATIONS	
It is anticipated that 3 to 4 subjects will be enrolled per month. It is expected that 12 months will be required to accrue the number of subjects necessary to complete the trial.
 
Treatment response will be assessed for each subject at 16 weeks. The null hypothesis is that the response rate (ie, sum of CR and PR) is $\leq 30\%$, & alternative hypothesis is that the response rate (RR) is $\geq 60\%$. The selection of 60% as a threshold for determining the treatment is worthy of further study is due to recent trials of sarcoma FDA approved drugs showing $\sim 60\%$ PFS rate at 3 months (ie, pazopanib, trabectedin, and eribulin).

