1. OBJECTIVES

1.1. Primary Objectives

- a. Assess whether the rate of clinical benefit is sufficiently high to merit promise for further study**

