2.4 Study Design

- The primary purpose for the protocol is treatment
- The interventional model is non-randomized single group
- One intervention arm
 - Ipilimumab 1 mg/kg with nivolumab 3 mg/kg every 3 weeks x 4 doses. (One cycle of treatment is 3 weeks)

- Cryoablation of at least one tumor mass between Cycle 1 to 2 of above immunotherapy
- Maintenance therapy with nivolumab 480 mg every 4 weeks (up to 24 months). (Each cycle of maintenance therapy is 4 weeks).
- Additional ablations are allowed per investigator's discretion
- Subject number: 30
- Primary endpoints
 - Clinical benefit (CR, PR, SD) based on the response evaluation criteria in solid tumors (RECIST) criteria v1.1 and Immune-related RECIST (irRECIST), assessed at 16 weeks.
- Secondary endpoints
 - 6-month progression-free survival
 - Safety and tolerability
 - Correlative measures (See below)

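### The primary endpoint is CR/PR/SD in Section 2.4 and the opening of Section 12, but the Simon rule tests CR+PR against a 60% target borrowed from 3-month PFS

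*Combined protocol and SAP*

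**What the plan says.** The text divides into two groups.

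- **Clinical benefit.** Section 1.1 sets the primary objective: "Assess whether the rate of clinical benefit is sufficiently high to merit promise for further study". It does not define benefit, and nor does the synopsis objective. Section 2.4 does, under primary endpoints: "Clinical benefit (CR, PR, SD) based on the response evaluation criteria in solid tumors (RECIST) criteria v1.1", with irRECIST named alongside and assessment at 16 weeks. The second paragraph of Section 12 says "clinical benefit (CR/PR/SD) will be assessed for each subject at 16 weeks" and moves directly to the 30% and 60% hypotheses.
- **CR+PR.** The next paragraph of Section 12 brings in the Simon design to address the primary objective, but defines what is tested as "The null hypothesis that the true response rate (ie, sum of CR and PR) is 30% or less". Its final rule counts CR or PR: if 12 or fewer of 28 patients "demonstrate a clinical response (either CR or PR), we will conclude the treatment is not worthy of further study". The synopsis statistics row also uses "the response rate (ie, sum of CR and PR" as the tested rate. Section 4 measures benefit by the objective response rate. Section 10.1, Outcome 1, counts CR+PR by 16 weeks under RECIST 1.1.

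A note in Section 10.1 declares a single primary outcome and says other objectives appear as secondary outcomes. Those include SD alone (Outcome 3), irRECIST response (Outcome 5) and 6-month PFS (Outcome 6). CR/PR/SD combined is not among them.

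The only reason given for 60%, in the synopsis and in Section 12, is "recent trials of sarcoma FDA-approved drugs showing ~60% PFS rate at 3 months". No source is given for 30%.

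**The concern.** The stage-1 stop and the final claim are the trial's only formal decisions. A reader of Section 2.4 would count a patient with stable disease as a success; a reader of the decision rule would count the same patient as a failure. With both readings in the plan, the more favourable count could be chosen after the data are seen.

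The target has a separate weakness, which remains even if CR+PR is confirmed. Under Outcome 6, PFS success means alive without progression, so stable disease qualifies. A PFS rate therefore says little about how many tumours should shrink. Section 2.3 puts response at 10–20% for conventional therapy and below 10% for pazopanib, which is one of the drugs cited for the 60%. The same drug appears at about 60% on one scale and under 10% on the other.

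**Working it through.** **Inputs (Section 12).** Stage 1: n₁ = 10, stop if 3 or fewer respond. Stage 2: 18 more, total 28; promising if 13 or more respond. p₀ = 0.30, p₁ = 0.60, one-sided; stated type I error 0.04 and power 90%.

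**Formulas.** With p the true rate of the counted event:

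- P(stop at stage 1) = P(Bin(10, p) ≤ 3)
- P(promising) = Σ over x = 4,…,10 of P(Bin(10, p) = x) × P(Bin(18, p) ≥ 13 − x)

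**Step 1: the plan's own figures.** At p = 0.30, P(promising) = 0.0419 (stated 0.04). At p = 0.60 it is 0.912 (stated 90%). Both reproduce. They depend only on the rate of whatever event is counted, so the limits have these error rates for either endpoint.

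**Step 2: the rule at other true rates.**

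| True rate of counted event | P(stop at stage 1) | P(promising) |
|---|---|---|
| 0.10 | 0.987 | <0.0001 |
| 0.15 | 0.950 | 0.0001 |
| 0.20 | 0.879 | 0.0012 |
| 0.30 | 0.650 | 0.042 |
| 0.40 | 0.382 | 0.268 |
| 0.50 | 0.172 | 0.655 |
| 0.60 | 0.055 | 0.912 |
| 0.70 | 0.011 | 0.988 |

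A CR+PR rate of 40% is twice the top of the protocol's 10–20% range. The trial would still stop early with probability 0.38 and declare promise with probability only 0.27.

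**Step 3: how often the two endpoints give different decisions.** Apply the same limits to both counts in the same patients. The CR+PR count never exceeds the CR+PR+SD count, so a pass on CR+PR implies a pass on CR/PR/SD. The probability of disagreement is therefore the difference between two rows of the table. For CR+PR 20% and benefit 60%: stage 1, 0.879 − 0.055 = 0.824; final claim, 0.912 − 0.001 = 0.911.

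The documents give neither rate for this regimen, so the pairs below are assumed.

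| CR+PR | Benefit (CR/PR/SD) | Stage-1 decisions differ | Final claims differ |
|---|---|---|---|
| 10% | 30 / 40 / 50 / 60% | 0.34 / 0.60 / 0.82 / 0.93 | 0.04 / 0.27 / 0.65 / 0.91 |
| 20% | 30 / 40 / 50 / 60% | 0.23 / 0.50 / 0.71 / 0.82 | 0.04 / 0.27 / 0.65 / 0.91 |
| 30% | 40 / 50 / 60% | 0.27 / 0.48 / 0.60 | 0.23 / 0.61 / 0.87 |
| 40% | 50 / 60 / 70% | 0.21 / 0.33 / 0.37 | 0.39 / 0.64 / 0.72 |

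**The case against.** The best reply is that the operative endpoint is already clear. Every passage that defines the tested rate, sets the final limit or declares the outcome uses CR+PR. No passage ties 3 of 10 or 12 of 28 to CR/PR/SD. Section 4 can be read as defining benefit through ORR, and Section 10.1 declares one primary outcome. On this view Section 2.4 and one sentence of Section 12 are stray wording, and the composite is roughly Outcome 1 plus Outcome 3.

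Much of this stands: the weight of the text favours CR+PR, and the disagreement figures apply the limits to a count the plan never formally adopts. But the Section 10.1 note does not correct Section 2.4, and a sum that a reader could form is neither a listed outcome nor a test.

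On the target, p₁ in a Simon design is a rate worth detecting, not a forecast, so exceeding historical rates is no flaw in itself. A pass probability of 0.001 at a true 20% is the design properly rejecting a rate below its null, and a 30% null is a demanding bar, not an error. Power is also at least 90% from a true rate of about 59.2% upward, not only at 60%. All of that is fair. What remains is that neither 30% nor 60% has a basis on the response scale.

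**Conclusion.** The concern holds and should be fixed. The primary endpoint as Section 2.4 defines it has no test, and the 60% target for the endpoint that is tested is justified by a different quantity. The limits are correct for 30% versus 60%.

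The consequence depends on the unknown CR+PR and SD rates. Over the assumed range, disagreement on the final claim runs from 0.04 (benefit 30%, CR+PR 10% or 20%) to 0.91 (benefit 60%, same CR+PR rates). Disagreement at stage 1 runs from 0.21 to 0.93, so it is not negligible anywhere in the range. These figures assume independent patients and the same limits for both counts. The textual conflict and the missing rationale need no such assumptions.

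**What to change.** Before stage-1 results are reviewed, name one primary measure and one set of criteria: RECIST 1.1, as in Outcome 1, or irRECIST, since Sections 2.4 and 4 name both. Use them in the synopsis (objective and statistics rows) and in Sections 1.1, 2.4, 4, 10.1 and 12.

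**Smallest change: keep CR+PR.**

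- Align the synopsis objective, Section 1.1, Section 2.4 and the opening of Section 12 with the existing rule.
- Add the CR/PR/SD rate as a secondary outcome.
- Delete the 3-month PFS argument.
- Justify 30% and 60% from response-rate data; if that cannot be done, restate p₀, p₁ and the limits.

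**If CR/PR/SD is chosen deliberately**, 3/10 and 12/28 keep their error rates for 30% versus 60%, but the plan must also:

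1. state the minimum duration for SD, which Appendix B (2.4.3) refers to and the protocol does not give, or say that SD is a status at a fixed time;
2. reconcile the 16-week assessment with the scan schedule, because Section 4 and the Study Calendar place the first scan at week 12 or week 14 and later ones every 12 weeks, with none at week 16;
3. explain why 60% would be promising when approved drugs are said to reach about that figure, albeit at 3 months.

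Items 1 and 2 also apply to CR/PR/SD as a secondary outcome.

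**Cost.** Keeping CR+PR takes a protocol amendment to the text, and no extra patients or scans unless p₀ or p₁ changes; the first on-treatment scan already falls before 16 weeks. Choosing CR/PR/SD replaces the declared outcome with a more lenient one and supports a weaker claim.

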1.3. Exploratory Objectives

- a. Correlate the mutation burden by NGS with response**
- b. Correlate PDL1 expression with response**
- c. Correlate tumor infiltrating lymphocytes/macrophages with response**

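### The exploratory biomarker regressions name no small-sample estimator: fitted by maximum likelihood they overstate the log odds ratio by about 20% on average at 28 subjects, and often have no finite estimate if the trial stops at 10

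*Combined protocol and SAP*

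**What the plan says.** Section 12 (repeated in the synopsis) gives the biomarker analysis in one sentence: "Generalized linear regression methods (with a logit link) will be utilized to characterize relationships between features such as mutation burden", with PD-L1 and immune-cell infiltration as the other named markers. It is the only method offered for the objectives in Section 1.3, which are listed one by one, for example "Correlate the mutation burden by NGS with response" and, as a separate item, "Correlate PDL1 expression with response". The plan does not name an estimator, the number of markers, whether markers enter singly or together, an interval method, or what to do when responders are few.

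The amount of data follows from the two-stage rule in the same section. Stage 1 has 10 subjects, and its stopping rule reads: "If 3 or fewer subjects (< 30% of 10 subjects) achieve a clinical response, the trial will be stopped for futility". Above that bound the trial goes on to stage 2, where the plan is that "we will enroll and treat an additional 18 subjects". At the end, the treatment is called promising if responses are seen in "more than 12 of the 28 treated subjects". The regressions will therefore use 10 subjects with 0 to 3 responders, or about 28 subjects.

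**The concern.** ML logistic regression has two known weaknesses in small samples. Its estimates are biased away from zero. It also has no finite estimate under separation, that is, when the marker divides responders from non-responders without overlap or when a 2x2 table has an empty cell. An unqualified logit-link model will normally be fitted by ML, so the numbers of subjects here expose the analysis to both.

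What is at stake is how the marker results read. Odds ratios would be too large on average. After an early stop there might be no usable estimate, and the analyst would then choose a remedy with the data in view.

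**Working it through.** **1. The plan's own design figures.** With bounds 3 of 10 and 12 of 28, the probability of a positive result is the sum over x = 4 to 10 of b(x; 10, p) × P(Bin(18, p) ≥ 13 − x). This gives 0.0419 at p = 0.30 (the plan states 0.04) and 0.912 at p = 0.60 (the plan states 90%). Both agree, so the sample sizes and bounds are read correctly. The plan gives no figure for the biomarker models.

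**2. How likely is an analysis of 10 subjects?** P(Bin(10, p) ≤ 3) is 0.65 at p = 0.30 and 0.055 at p = 0.60. At 20% and 10%, the ends of the range that Section 2.3 gives for conventional therapy, it is 0.88 and 0.99.

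**3. Exact failure rate of ML after a stop, one marker unrelated to response.** For a continuous marker with r responders out of 10, the chance of separation is 2/C(10, r). For a binary marker with 4 of 10 positive (assumed), it is the hypergeometric chance of an empty cell, [C(6, r) + C(4, r)]/C(10, r) for r = 2 or 3. With r = 1 a cell is always empty. With r = 0 there is nothing to fit.

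| Responders | Probability at 30% response | Continuous | Binary |
|---|---|---|---|
| 0 | 0.0282 | 1 | 1 |
| 1 | 0.1211 | 2/10 = 0.200 | 1 |
| 2 | 0.2335 | 2/45 = 0.044 | 21/45 = 0.467 |
| 3 | 0.2668 | 2/120 = 0.017 | 24/120 = 0.200 |

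The probabilities sum to 0.6496. Averaged over stopped trials:

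- continuous: (0.0282 + 0.0242 + 0.0104 + 0.0044)/0.6496 = 0.10
- binary: (0.0282 + 0.1211 + 0.1090 + 0.0534)/0.6496 = 0.48

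No effect size is assumed here. A real association raises both figures.

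**4. The same with an association.** Trials were simulated along the two-stage path at 30% response. The continuous marker was standard normal with a true log odds ratio of about 0.70; the binary marker was 40% positive on average with an odds ratio of 2. Among trials stopped at 10 subjects, ML has no finite estimate in about 14-17% with one continuous marker and 52% with one binary marker. Where the continuous estimate is finite, ML averages 1.21 (median 0.75) and Firth averages 0.64 over its fits, against a true 0.69.

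**5. At 28 subjects.** Exact separation for one null continuous marker with 8 responders is 2/C(28, 8), effectively zero. For a null binary marker (11 of 28 positive) with 8 responders it is 0.8%. In simulation at 30-60% response, ML fails in 0-0.1% of fits with continuous markers and 0.4-5% with binary ones; the upper end of the binary range comes from three markers in one model.

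The bias with one continuous marker, 30% response and true value 0.70 is:

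| | Mean | Root mean squared error |
|---|---|---|
| ML | 0.85 | 0.69 |
| Firth | 0.71 | 0.53 |

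The relative bias of the ML mean is 0.85/0.70 − 1 = 21%. The ML median is 0.77, so 0.77/0.70 − 1 = 10%: part of the mean bias comes from a few nearly separated datasets. With one binary marker the ML mean is 0.72-0.74 against 0.69, so the bias is smaller.

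**6. What penalisation does not cure.** The ratio of upper to lower limit of a typical 95% Wald interval for the odds ratio, computed from the Firth standard error at 30% response, is about 6 (continuous) or 26 (binary) at 28 subjects, and about 42 or almost 800 at 10.

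The simulations used 600 to 3,000 replicates, with Monte Carlo error of about 1-2 percentage points on the failure rates and more in sparse cells.

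**The case against.** The strongest reply is that Section 12 does not prescribe ML. A Firth fit is still a logit-link regression, so the remedy is compatible with the text. That stands: this is an unspecified estimator, not a wrong method written into the plan. The sentence still leaves the default in place, and the default is ML.

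A reader might also infer that several markers go into one model, where bias and failure are worse. The documents do not say so. Section 1.3 lists the objectives separately, and single-marker models fit the wording equally well. The point is therefore sized on one marker.

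A reader might infer that odds ratios will often fail to exist in the full trial. They will not: at 28 subjects and 30-60% response this is rare, and an early stop is itself unlikely if the true rate is 60%.

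The bias at 28 subjects is also small beside the sampling error. It is about 0.15 on the mean and 0.07 on the median, against a standard error of about 0.5, and a reported interval would show that imprecision. This too stands and is why the point is minor. Firth's fit nevertheless lowers both bias and total error, at almost no cost.

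**Conclusion.** The concern holds as a minor, inexpensive improvement to an exploratory analysis. With 28 subjects and one continuous marker, ML overstates the log odds ratio by about 20% on average and 10% at the median. After a stage-1 stop it gives no finite estimate in about 14-17% of datasets with one continuous marker and in about half with one binary marker.

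These sizes rest on assumptions that are not in the documents: a normal marker or one 40% positive, an odds ratio of about 2, and mainly a 30% response rate. They also take response as CR plus PR, as in the decision rule. Sections 2.4 and 12 also describe an endpoint that includes stable disease, which would change the number of events.

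Two stronger readings are not supported. Nothing in the documents says that these estimates will select markers for a later study; Section 12 attaches no test, power claim or decision to them. Nor would penalisation make the results reliable at 10 subjects, where intervals are too wide to inform and a trial with no responders says nothing about markers. The two-stage decision is untouched.

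**What to change.** Add to Section 12, and to the matching synopsis text, a statement to this effect: each marker will be analysed in its own logistic model, fitted by Firth's penalised likelihood, with profile-penalised-likelihood confidence intervals; results are hypothesis-generating estimates; if the trial stops after stage 1, marker values will be shown by response descriptively and no model will be fitted. State in the same place which definition of response the models use.

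The cost is a sentence or two and standard software, with no change to sample size, data collection or the primary rule. The drawbacks are slight shrinkage toward zero (Firth median 0.67 against a true 0.69 at 28 subjects with one continuous marker), intervals that are less familiar to readers, and precision that remains poor.
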